### 9.3 VARIABLES

#### 9.3.1 Data points

Table 9.3.1:1 Flowchart for Objective 1

Data collection time point	Baseline	At hospital discharge (or 14 days)
Informed consent	X	
Review of in- / exclusion criteria	X	
Demographics	X	
Medical history	X	
VTE disease characteristics	X	X
Treatment for VTE	X	X
Height	X	
Weight	X	
Blood pressure and heart rate	X	
Collect Laboratory data (if available)	X	
Adverse drug reactions (ADR) 	X	X
Adverse events with fatal outcomes 	X	X
Concomitant therapy	X	
Completion of patient participation		X

1. Data will be collected at the date of hospital discharge or at 14 days post diagnosis, whichever is later.
2. For collection and reporting of ADRs and AEs with fatal outcome please refer to [Section 11.2.](#)

Table 9.3.1:2 Flowchart for Objective 2

Data collection time point	Baseline	At hospital discharge (or 14 days) 	3 months	6 months	1 year
Informed consent	X				
Review of in- / exclusion criteria	X				
Demographics	X				
Medical history	X				
VTE disease characteristics	X	X			
Treatment for VTE	X	X	X	X	X
Concomitant diseases		X	X	X	X
Height	X				
Weight	X		X	X	X
Blood pressure and heart rate	X				
Collect Laboratory data (if available)	X	X	X	X	X
Adverse drug reactions (ADR) 	X	X	X	X	X
Adverse events with fatal outcomes 	X	X	X	X	X
Outcome events	X	X	X	X	X
Morisky Medication Adherence Scale			X	X	X
Health resource utilization			X	X	X
PACT-Q2			X	X	X
Concomitant therapy	X	X	X	X	X
Completion of patient participation					X
Vital status collection 			X	X	X

1. Data will be collected at the date of hospital discharge or at 14 days post diagnosis, whichever is later
2. For collection and reporting of ADRs and AEs with fatal outcome please refer to [Section 11.2.](#)
3. Vital status will be collected if the patient declines further clinic visits. See also [9.3.3.](#)

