### 9.3.2 Outcome measures

For [Objective 1](#):

The following primary outcome measures will be analyzed on data that is collected at the time of the acute VTE event:

- Demographic information (age and gender)
- VTE event information (event type and treatment for event)

The following further outcome measures will be analyzed on the collected baseline data:

- co-medication
- co-morbidities,

- basic physical examination data
- laboratory information
- VTE event information including location, extent and severity of the thrombus
- VTE risk factors
- history of VTE event
- bleeding risk

For [Objective 2](#):

The following primary outcomes will be analyzed from time of diagnosis of the index event to 12 months post diagnosis:

- Primary safety outcome measure: ISTH Major bleeding and ISTH clinically relevant non major bleeding (CRNMB)
- Primary effectiveness outcome measure: symptomatic recurrent VTE including VTE-related mortality

The following secondary outcomes will be analyzed from the time of diagnosis of the index event to 12 months post diagnosis:

- Recurrent DVT and/or PE
- VTE-related mortality
- All-cause mortality

The following further outcomes will be analyzed from time of diagnosis of the index event to 12 months post diagnosis:

- Life-threatening bleeding events
- Acute coronary syndrome (ACS)
- Serious adverse drug reactions
- Net clinical benefit (NCB)
- Satisfaction with anticoagulation treatment (PACT-Q2)
- Health care resource utilization

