- STEMI: must have cardiac marker evidence of myocardial necrosis (e.g. positive cardiac troponin (Tn) or creatinine kinase isoenzymes CKM and CKB (CK-MB)) and new (or presumably new, if no prior electrocardiogram (ECG) is available) ST segment elevation or left bundle branch block on admission ECG.
- NSTEMI: will have cardiac marker evidence of myocardial necrosis (positive Tn or CK-MB) without new ST segment elevation.
- UA: is angina pectoris with any 1 of the 3 following features:
  - Angina occurring at rest and prolonged (usually  $\geq 10$  min)
  - New-onset angina of at least Canadian Cardiovascular Society (CCS) classification III severity
  - Recent acceleration of angina reflected by an increase in severity of at least 1 CCS class to at least CCS class III. The patient must also not have any biochemical evidence of necrosis.

Serious adverse drug reactions: refer to Section [11.1](#) and [11.2](#) for serious criteria and reporting requirements.

NCB: the event rate of recurrent symptomatic VTE or VTE-related mortality plus the major bleeding event rate will be compared for dabigatran etexilate versus VKA. [[P14-17361](#)]

Treatment adherence: adherence will be assessed using the [Morisky Medication Adherence Scale](#).

Treatment persistence: will be assessed as time from treatment onset until permanent treatment discontinuation.

Exposure: will be assessed based on the anticoagulation treatment start date, dosage and the reported end date.

Perception of anticoagulation treatment satisfaction will be assessed using the PACT-Q2 (administered at follow-up time-points for those patients followed under [Objective 2](#)).

Health care resource utilization will be assessed as number of hospital admissions, emergency room visits, and physician's office visits calculated per-patient-per-month to account for variable follow-up time.

Vital status: if a patient is enrolled for follow-up ([Objective 2](#)) and then declines to return for clinic visits, the patient's vital status should be collected and reported after one year. If any outcome events (e.g., bleeding events, recurrent VTEs or other adverse drug reactions (ADRs)) occur, details should be recorded in the electronic Case Report Form (eCRF) and reported as appropriate. If the patient died, available data (e.g. date of death, cause of death) should be reported.

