5.2 SECONDARY OUTCOMES

The following secondary outcomes will be analysed from the time of diagnosis of the index event to 12 months post diagnosis:

- Recurrent DVT and/or PE
- VTE-related mortality
- All-cause mortality

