7.6 MAIN ANALYSIS

Analyses for the main outcome events are mainly defined for patients in the restricted patient set and, in some occasions for patients in the eligible patient set who took at least once the treatment. In general, recurrent events will be disregarded for the analyses of the outcomes.

Main outcome events – Incidence rates

For the treatment groups incidence rates with 95% CIs, cumulative risks, and KM curves will be calculated on the eligible patient set. Only patients from the eligible patient set that took the prescribed treatment at least once are considered. Patients who complete the planned anticoagulation treatment prior to one year or discontinue initial anticoagulation treatment permanently will be censored at date of last drug intake + 6 days for both DE and VKA or at first intake of another relevant anticoagulation treatment, whichever occurs first. A patient is considered to have permanently stopped initial anticoagulation treatment if other relevant anticoagulation treatment is initiated or if treatment has been interrupted for more than 30 days.

The main analysis of overall incidence rates with 95% confidence intervals, cumulative risks and KM curves will be repeated for the subgroups defined in Section 6.4. A graphical (forest-plot-like) display will additionally be prepared to summarize the subgroup results per outcome on the eligible patient set. Additional subgroup analyses might be conducted as needed.

For all important main and secondary outcomes for patients initiating VKA at baseline, and patients initiating DE at baseline, incidence rates, cumulative risks with 95%-confidence intervals will be calculated by treatment, and for a graphical comparison Kaplan Meier curves

will be plotted. These statistics will be calculated on the restricted patient set, and patients who never took the prescribed treatment will not be included. For the restricted patient set, as a sensitivity analysis, the calculation of incidence rates and cumulative risks will be performed without censoring at permanent discontinuation (intention to treat (ITT) approach). KM curves will be plotted.

Secondary and further outcome events

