Immobilization	True or False (CRF categories, medical history and concomitant diseases will be manually reviewed (past and concomitant))	N/A
Thrombophilia	True or False (CRF categories, medical history and concomitant diseases will be manually reviewed (past and concomitant))	N/A
Pregnancy and peri-partum period	True or False (CRF categories, medical history and concomitant diseases will be manually reviewed (3 month time window))	N/A

Concomitant use of aspirin	True or False (concomitant medication and other VTE therapies will be manually reviewed (concomitant))	N/A
Concomitant use of clopidogrel	True or False (concomitant medication and other VTE therapies will be manually reviewed (concomitant))	N/A
Estrogen therapy	True or False (concomitant medication and other VTE therapies will be manually reviewed (3 month time window))	N/A
Concomitant cancer	True or False (CRF categories, medical history and concomitant diseases will be manually reviewed (concomitant))	N/A
Hypertension	True or False (CRF categories, medical history and concomitant diseases will be manually reviewed (concomitant))	N/A
History of previous VTE	True or False (CRF categories, medical history and concomitant diseases will be manually reviewed (regardless of timing))	N/A
History of major bleeding or prior gastrointestinal bleed	True or False (medical history and concomitant diseases will be manually reviewed (regardless of timing))	N/A
Chronic renal disease	True or False (CRF categories, medical history and concomitant diseases will be manually reviewed (concomitant))	N/A

Patients who complete the planned anticoagulation treatment prior to one year or discontinue initial anticoagulation treatment permanently will be censored at date of last drug intake + 6 days for both dabigatran etexilate and VKA or at first intake of another relevant anticoagulation treatment, whichever occurs first. A patient is considered to have permanently stopped initial anticoagulation treatment if other relevant anticoagulation treatment is initiated or if treatment has been interrupted for more than 30 days.

Multiple imputation methods (e.g. the fully conditional specification method) will be used to impute both continuous and categorical variables appropriately with arbitrary missing patterns.

- b.) In addition, Cox regression analysis (based on the main analysis model) will be performed without censoring at permanent discontinuation (intention to treat (ITT) approach).

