3.) Analyses of secondary and further outcome events

The same Cox regression model as used for the primary outcomes will be used for the secondary and further outcomes, if enough events are reported. The ePS overlap weights analysis on the specific outcome event might be performed for all outcomes.

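### All-cause mortality runs to 12 months, but the only adjusted model planned for it appears to censor at treatment stop or switch

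*SAP*

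**What the plan says.** **Outcome window.** Protocol 9.3.2 lists all-cause mortality under this sentence: "The following secondary outcomes will be analyzed from the time of diagnosis of the index event to 12 months post diagnosis". SAP (Objective 2) 5.2 keeps the same window, "from the time of diagnosis of the index event to 12 months post diagnosis".

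**Data.** Under Protocol 9.2.4 (Follow-up), Objective 2 patients who stop or switch anticoagulants remain in follow-up. For a patient who declines clinic visits, Protocol 9.3.3 says "the patient's vital status should be collected and reported after one year". The footnote to Table 9.3.1:2 agrees: "Vital status will be collected if the patient declines further clinic visits".

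**Model for death.** SAP 7.6 item 3: "The same Cox regression model as used for the primary outcomes will be used for the secondary and further outcomes", provided there are enough events. Overlap weighting for these outcomes is mentioned only as a possibility. No censoring rule specific to death is given.

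**Censoring.** Protocol 9.7.2.1 makes the primary comparisons as treated. SAP 7.6 repeats the rule: patients who finish early or stop permanently "will be censored at date of last drug intake + 6 days for both DE and VKA", or at first intake of another relevant anticoagulant if that comes sooner. A stop is permanent if there is a switch or an interruption longer than 30 days.

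**Uncensored analyses.** Item 2b is a Cox analysis built on the main model that "will be performed without censoring at permanent discontinuation (intention to treat (ITT) approach". It sits under item 2, whose title names the two main outcomes only. Earlier in 7.6, incidence rates, cumulative risks and Kaplan-Meier curves are also planned without this censoring in the restricted set. The text just before that covers main and secondary outcomes.

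**The concern.** In a non-randomised comparison, the adjusted estimate is the one readers will interpret. For death, stopping the anticoagulant can itself be a sign that death is near, so censoring shortly after the last dose is plausibly informative. Overlap weights balance baseline covariates. They do not correct for censoring driven by deterioration after baseline.

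Two things are at stake. If withdrawal before death is more common in one arm, the mortality hazard ratio partly reflects stopping behaviour, and the direction cannot be known in advance. If it is equally common in both arms, the ratio is roughly preserved, but deaths are lost and the absolute 12-month risk implied by the adjusted analysis is too low.

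**Working it through.** **1. Does the model for death censor?** The item 1 text on the overlap-weighted model does not say so. Two other places do, indirectly. Protocol 9.7.2.1 defines the primary comparison as treated with the 6-day rule. Item 2b describes its own analysis as the main model with that censoring removed, so the main model must contain it. Item 2a (multivariable Cox) is followed by the rule in full. Whichever of the two models item 3 means, the result is censored.

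**2. Which deaths enter which analysis?**

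| Death occurs | Adjusted Cox, item 3 (inferred) | Unadjusted uncensored rates and curves |
|---|---|---|
| On drug, or within 6 days of last dose | counted | counted |
| More than 6 days after a completed course | left out | counted |
| After a switch | left out | counted |
| After an interruption of more than 30 days | left out | counted |
| 7 to 30 days after last dose, no switch, course not completed | ambiguous | counted |

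In the last row the patient has neither switched nor been off drug for more than 30 days, so literally has not permanently stopped. A patient who survives past day 30 is, by contrast, censored back at day 6.

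**3. Time at risk for completers.** Inclusion criterion 4 requires planned treatment of at least 3 months. With the SAP 6.7 conventions (month 3 = 91 days, month 6 = 182, year 1 = 365):
- stop at 3 months: (91 + 6)/365 = 97/365 = 27% of the year;
- stop at 6 months: (182 + 6)/365 = 188/365 = 52%.

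**4. Deaths within 6 days of a withdrawal made because the patient is dying.** Assume an exponential lag from last dose to death with mean m. Then P(lag ≤ 6) = 1 − exp(−6/m): 45% for m = 10 days, 25% for m = 21, 12% for m = 45.

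**5. Illustrative size.** The plan has no mortality figure to reproduce. Its only Objective 2 power statement (5,000 patients, 90%) concerns bleeding. It reproduces at 88.9% with the Freedman formula and 15% exponential loss, and this point does not affect it.

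All inputs below are assumptions: 5,000 patients, 1:1, equal true 12-month mortality of 5% (5000 × 0.05 = 250 deaths), 50% stopping within the year at a constant rate for unrelated reasons, mean lag 21 days. SE(log HR) ≈ 2/√deaths; with all 250 deaths it is 0.126.

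| Share of dying patients withdrawn beforehand | Deaths counted at last intake + 6 days | SE(log HR) | Increase |
|---|---|---|---|
| 0% | 184 (73%) | 0.147 | 17% |
| 30% | 143 (57%) | 0.167 | 32% |
| 50% | 116 (46%) | 0.186 | 47% |

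In the last row, mean lags of 45 to 10 days give 42% to 54%. Mortality of 3% or 10% gives the same shares. Extending the cut-off to 30 days after the last dose would count 170 of 250 (68%) instead of 116, which shows how much the unclear 7-to-30-day window matters.

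Rate ratio, dabigatran to VKA, using time at risk and the 6-day cut-off (true value 1.0):
- equal withdrawal in both arms: about 1.0;
- 60% dabigatran versus 40% VKA: about 0.80 (0.74 to 0.86 over the same lags);
- reversed: about 1.26 (1.16 to 1.34).

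**The case against.** The sponsor has a fair reply. The 12-month window can be read as a maximum horizon: Protocol 9.3.2 gives it to the primary outcomes too, and those are analysed as treated. Leaving out deaths after a completed course is what an on-treatment analysis means, and choosing that for a secondary outcome is a choice of estimand. The study is declared exploratory (Protocol 9.7.1). VTE-related deaths already enter item 2b through the effectiveness composite. All of this stands, and it limits the point to a missing analysis.

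Four stronger readings are tempting but are not supported:
- *The 12-month mortality is never estimated.* Uncensored rates, cumulative risks and curves by arm are planned, and the wording reaches secondary outcomes. They are only unadjusted.
- *A patient taken off drug for palliative care who dies a week or two later is certainly censored alive.* The 30-day definition leaves this case open.
- *Vital status is collected for the mortality analysis.* It is obtained only when visits are declined, and no analysis is named for it.
- *Unequal numbers of counted deaths show a biased hazard ratio.* Counts ignore time at risk. If equal constant hazards give 50 and 70 counted deaths because the arms spend 50% and 70% of the year on drug, the rate ratio is (50/0.5)/(70/0.7) = 1.00. Bias needs withdrawal because of approaching death to differ by arm.

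**Conclusion.** The point holds as a gap in the plan. No adjusted comparison of all-cause mortality is planned without on-treatment censoring, although the outcome is defined to 12 months and follow-up continues after treatment stops. That the item 3 model censors is an inference from Protocol 9.7.2.1 and item 2b, but a firm one.

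The size is unknown, because the documents give neither mortality nor withdrawal rates. The figures above show only what plausible assumptions imply: a loss of roughly a quarter to a half of the deaths, and a distortion in either direction if withdrawal before death differs between arms. If it does not differ, the harm is to precision and absolute risk, not to the ratio. This is a cheap and worthwhile improvement to a secondary, exploratory analysis. Whether the uncensored model should replace the as-treated one as the main mortality analysis is debatable, and the point does not depend on it.

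**What to change.** In SAP (Objective 2) 7.6:
- Extend item 2b to all-cause mortality: the overlap-weighted Cox model without censoring at discontinuation or switch, following each patient to death, last known alive (including the vital-status contact) or 12 months. Do the same for VTE-related mortality on its own if events allow.
- Report it beside the as-treated result.
- State the censoring rule for each outcome, and say how deaths 7 to 30 days after the last dose are handled.

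The cost is some SAP wording and one more run of a model already planned, on data the protocol already collects. The downside is that late deaths after stopping or switching dilute any on-drug effect; the as-treated result, kept alongside, still shows that effect.

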7.8 EXPOSURE TIME

Exposure data will be summarized based on the eligible and restricted patient sets for dabigatran etexilate and VKA. Prescribed but never taken patients will be excluded from all the analyses described in this section.

The total exposure time will be calculated for each treatment group X as:

Exposure treatment X[days]=last date of treatment intake – first date of treatment intake + 1

The calculated days are converted to months (12*days/365.25) for summary tables.

In addition, total patient years will be calculated and presented:

Total patient – years treatment X[years] = \sum_{Patients} Exposure treatment X [days]/365.25.

7.9 SAFETY ANALYSES

7.9.1 Adverse events

Analyses for AEs will be based on the all eligible treated patient set. The analysis of adverse events will be descriptive in nature and will be based on BI standards (see DM&SM: Handling and summarization of adverse event data for clinical trial reports and integrated summaries [6]). Adverse events will be coded with the most recent version of MedDRA. The summary of standard AE tables will be based on the AE/ SAE CRFs. According to the reporting procedures for this study, all SAEs and outcome events are to be documented on the SAE or outcome events form irrespective of causal relationship to antithrombotic treatment or any other BI drug. Non-serious AEs which are not deemed related to antithrombotic treatment or to any other BI drug should not be included in the CRF (see study protocol, Section 11.2).

For the analysis, only AEs which are considered treatment-emergent for antithrombotic treatment are included.

For analysis of adverse drug reactions (ADRs), all AEs which are related to antithrombotic therapy according to the investigators' judgment are to be included.

The following tables will be created by treatment group:

- Overall summary of ADRs.
- Frequency [N (%)] and incidence rate (per 100 patient years) of patients with ADRs (related to antithrombotic therapy).
- Frequency [N (%)] and incidence rate (per 100 patient years) of patients with ADRs (related to antithrombotic therapy) leading to discontinuation of antithrombotic treatment.
- Frequency [N (%)] and incidence rate (per 100 patient years) of patients with ADRs (related to antithrombotic therapy) leading to death.
- Frequency [N (%)] and incidence rate (per 100 patient years) of patients with Serious ADRs (related to antithrombotic therapy).
- Frequency [N (%)] and incidence rate (per 100 patient years) of patients with fatal AEs

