### **9.2.3 Removal of subjects from the study**

A patient can be withdrawn from the study for the following reasons:

1. A patient withdraws consent, without the need to justify the decision.
2. The patient was erroneously included in the study.

Boehringer Ingelheim (BI) reserves the right to discontinue the study overall or at a particular study site at any time for the following reasons:

1. Failure to meet expected enrollment goals overall or at a particular study site
2. Emergence of any efficacy/safety information that could significantly affect continuation of the study,
3. Violation of applicable sections of Good Clinical Practice (GCP), Good Pharmacoepidemiology Practice (GEP), the study protocol, or the contract by a study site or investigator.

The investigator / the study site will be reimbursed for reasonable expenses incurred in case of study termination (except in case of the third reason).

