### **9.7.2 Planned analyses**

Analyses will be performed by BI or BI's designees.

The main analysis population will consist of all eligible patients (i.e., all patients who provide informed consent and fulfill all inclusion criteria and no exclusion criteria).

Summary statistics for continuous variables will include the N, mean, standard deviation, minimum, Q1 (lower quartile), median, Q2 (upper quartile), and maximum value; tabulations of categorical variables will include all possible categories and will display the number of observations per category as well as percentages based on the relevant denominators. Estimates from statistical models will be presented with 95% CIs.

Additional details of the planned analysis will be provided in the statistical and epidemiological analysis plan (SEAP).

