### 9.7.2.3 Safety analyses

Statistical analysis and reporting of safety data will be descriptive in nature, will be based on BI standards, and will focus on ADRs to dabigatran etexilate or VKA. No hypothesis testing is planned.

Occurrences of ADRs will be analyzed relative to the number of patients treated as well as observed person-years (i.e., time at risk). Safety analysis will be based on the concept of treatment emergent ADRs. Patients will be analyzed according to the anticoagulation treatment received at the time of the event. If no concurrent anticoagulation treatment is administered, then events occurring within a washout period of 6 days after discontinuation of anticoagulation treatment will be assigned to the last treatment given. This washout period will also be included as time at risk for derivation of total person-years. ADRs that deteriorate under treatment will also be considered as “treatment emergent”. Events occurring prior to first intake of anticoagulation treatment prescribed at baseline, during periods without any anticoagulation treatment (excluding washout periods), or after the end of the 1 year follow-up (excluding washout periods) will not be considered treatment emergent events and will not be included in the summary tables.

The following parameters will be included in the safety analyses:

- Adverse drug reactions
- Adverse drug reactions leading to discontinuation of anticoagulation treatment
- Serious adverse drug reactions
- Adverse drug reactions leading to deaths

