#### Adverse drug reaction

An adverse drug reaction is defined as a response to a medicinal product which is noxious and unintended. Response in this context means that a causal relationship between a medicinal product and an adverse event is at least a reasonable possibility. Adverse drug reactions may arise from use of the product within or outside the terms of the marketing authorization or from occupational exposure. Conditions of use outside the marketing authorization include off-label use, overdose, misuse, abuse and medication errors.

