6.3 PATIENT SETS ANALYSED

Three patient sets are defined: "all eligible", "all eligible treated", and "restricted"; the following rules are used to assess if a patient is included in an analysis set:

ALL ELIGIBLE: If a patient fulfills all inclusion criteria and no exclusion criteria.

ALL ELIGIBLE TREATED: If a patient fulfills all inclusion criteria and no exclusion criteria and took prescribed treatment at least once.

RESTRICTED: The restricted population is composed of all eligible patients within the trimmed patient set which lie within the region of propensity score overlap (for definition see Section 7). As the propensity score analysis will be based on eligible patients who at least once took the prescribed treatment, the restricted population excludes patients prescribed the treatment but who did not take it.

Number of patients included in the different patient sets will be shown by treatment group.

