7. PLANNED ANALYSIS

The propensity scores will be estimated after the multiple imputation is performed based on eligible patients who took the prescribed treatment at least once. A logistic regression model will be used to model the probability of receiving dabigatran etexilate in comparison to vitamin K antagonist, i.e. high propensity scores, close to 1, indicate a higher probability of dabigatran use. See Section 7.6 for details.

For the main analysis, only those patients will be included who have a shared range of ePS. This patient set is denoted as the **restricted patient set in the SEAP**. Patients with ePS outside the overlapped ePS range will be trimmed (or excluded).

Safety analyses will be conducted for the all eligible treated patient set.

Summary statistics for continuous variables will include the number of observations (N), mean, standard deviation (SD), minimum, Q1 (25th percentile), median, Q3 (75th percentile), and maximum; tabulations of categorical variables will present all possible categories and will display the number of observations per category as well as percentages. The default precision for percentages should be one decimal place, unless otherwise specified. In general, percentages will be based on the number of patients eligible for the particular analysis, whether they have missing data or not. A category 'Missing' will be displayed whenever at least one patient falls within this category.

Data collected in the baseline eCRFs (informed consent, patient status, demographics, inclusion/exclusion criteria, vital signs and physical assessment, clinical signs and symptoms) will be considered as respective baseline values. Data collected in the hospital discharge related eCRFs will be summarized for the hospital discharge time point. Despite the fact that the analysis is of cross-sectional nature, data collected in eCRFs at hospital discharge will also be summarized in the descriptive analysis.

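### The Objective 2 adverse reaction and fatal event tables cover only eligible treated patients, so events in treated patients later judged ineligible have no stated place in the safety results

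*SAP*

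**What the plan says.** **Objective 2 SAP.** Section 7 sets the general rule: "Safety analyses will be conducted for the all eligible treated patient set". Section 7.9.1 repeats it for adverse events: "Analyses for AEs will be based on the all eligible treated patient set". Section 6.3 opens with "Three patient sets are defined" and describes the one used for safety as follows: "If a patient fulfills all inclusion criteria and no exclusion criteria and took prescribed treatment at least once". Section 7.8 summarises exposure on the eligible and restricted sets.

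**Protocol.** Section 9.7.2 states "The main analysis population will consist of all eligible patients". Its safety subsection, 9.7.2.3, states "Occurrences of ADRs will be analyzed relative to the number of patients treated as well as observed person-years" and adds no eligibility condition. Section 9.2.3 foresees ineligible enrolments, since one reason for withdrawal is "The patient was erroneously included in the study". Section 11.2 starts adverse drug reaction (ADR) collection for Objective 2 once consent is obtained and does not limit it to eligible patients.

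**The concern.** Restricting to eligible patients protects the DE versus VKA comparison. It does less for a description of reactions among people who actually took the drug. Here the restriction applies to every safety table, including serious ADRs, ADRs leading to death and fatal adverse events, and nothing in the supplied text picks up the patients it removes.

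Two features make this worth attention in a post-authorisation safety study. First, some inclusion criteria in protocol 9.2.1 could be judged failed after treatment has begun: the intended duration of at least three months, and availability for follow-up. If that judgement were made after an early event, removal would be linked to outcome. Protocol 9.2.4 asks sites not to exclude patients because of early outcome events, and an eligibility filter at analysis could undo that. Second, expedited reporting in protocol 11.2 covers DE only. For a VKA patient judged ineligible, an ADR goes to the eCRF, and the Objective 2 SAP names no output in which it would be seen.

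**Working it through.** The point rests on set definitions, and the plan gives no figure to reproduce. The steps are to trace the set, compare it with what is collected, and bound the effect.

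**1. Which patients can be tabulated.** SAP 7.9.1 leads to SAP 6.3, where the three sets are:

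| Set | Must be eligible? | Must have taken the drug? |
|---|---|---|
| All eligible | Yes | No |
| All eligible treated | Yes | Yes |
| Restricted (propensity score overlap) | Yes | Yes |

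Eligibility is a condition of all three. A treated patient who fails one criterion is in none of them, and so is absent from all six outputs listed in 7.9.1. The exposure summaries in 7.8 omit the same patients.

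**2. What is collected.** Protocol 11.2 (Objective 2) takes DE and VKA reactions from the time of the VTE, conditional on consent. Deaths are less uniform. The Objective 2 eCRF list in 11.2 names ADRs only, and the expedited form covers fatal events in DE-exposed patients. For VKA patients, fatal events rest on the flowchart (Table 9.3.1:2, all time points) and on vital status (9.3.3). None of these carries an eligibility condition.

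**3. Whether a listing fills the gap.** The Objective 1 SAP, 7.9.1, promises an appendix listing of all reported ADRs and fatal events, but Objective 1 ends at hospital discharge or 14 days. The supplied Objective 2 SAP text promises no such listing.

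**4. What the protocol requires.** Section 9.7.2 fixes an eligible main population, and 9.7.2.3 sits beneath it. Section 9.7.2.3 speaks of patients treated and names the events to be left out: those before first intake, in untreated periods outside washout, or after the one-year follow-up. Ineligibility is not among them. A set of eligible, treated patients is compatible with both passages, and a set of all treated patients fits the wording of 9.7.2.3 at least as well.

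**5. Size, under assumptions.** Inputs:
- N = 5,000, the upper planned size in protocol 9.5, with all patients taken as treated.
- f, the ineligible share, assumed to be 1% to 5%.
- k, the risk in ineligible relative to eligible patients, assumed to be 1 to 3.

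Patients left out = N × f: 5,000 × 0.01 = 50; 5,000 × 0.05 = 250.

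Proportion in all treated patients ÷ tabulated proportion = (1 − f) + f·k = 1 + f(k − 1).

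Share of patients with an event who are missing = f·k ÷ [1 + f(k − 1)].

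| f | k | Ratio of proportions | Share missing |
|---|---|---|---|
| 1% | 1 | 1.00 | 0.01 ÷ 1.00 = 1.0% |
| 1% | 3 | 1 + 0.01 × 2 = 1.02 | 0.03 ÷ 1.02 = 2.9% |
| 5% | 1 | 1.00 | 0.05 ÷ 1.00 = 5.0% |
| 5% | 3 | 1 + 0.05 × 2 = 1.10 | 0.15 ÷ 1.10 = 13.6% |

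For scale only, a tabulated 6.5% would be 6.5 × 1.10 = 7.15% in all treated patients in the last row. The 6.5% is the mean of the planning bleeding rates, (5.3 + 7.7) ÷ 2. It is not an ADR rate.

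**The case against.** The strongest reply is that the sponsor did what the protocol says. The main population is eligible patients, the safety analysis is descriptive with no hypothesis test, and relating ADRs to patients treated and to person-years can be read as naming two denominators and not a new population. A reader might infer that the SAP departs from the protocol; given 9.7.2, the documents do not support that.

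A reader might also infer that off-label use is filtered out, because protocol 11.1 says "Adverse drug reactions may arise from use of the product within or outside the terms of the marketing authorization". That does not follow. The entry criteria contain no dose, label or contraindication test, so off-label patients stay in the tables. Nor does early stopping make a patient ineligible, since the criterion concerns planned duration.

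Other replies stand in part:
- **Few patients.** Protocol 9.2.2 expects minimal numbers, but that sentence covers the exclusion criteria and not failed inclusion criteria.
- **No lost signal for DE.** Expedited reporting of DE reactions and of deaths in DE-exposed patients does not depend on eligibility. This is correct, and it limits the gap to the study's own reported safety results. It does not help VKA patients.
- **Harder attribution.** Patients anticoagulated for another condition, or on an investigational drug, blur attribution to DE or VKA, and withdrawn patients may have short follow-up. This argues for showing both sets, not for showing only one.
- **Unseen rules.** Deviation handling is in a separate Protocol Deviation Specification that was not supplied, and SAP 5.3, 6.4 and 7.7 are cited but not in the text. A handling rule there cannot be excluded; it would have to be reconciled with the set named in SAP 7 and 7.9.1.

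**Conclusion.** The point holds as a weakness in the choice of safety set. On the supplied text, ADRs and deaths in consenting, treated, ineligible Objective 2 patients have no table or listing. It is not a contradiction between SAP and protocol, and it does not touch the comparative outcome analyses.

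The size is unknown. Under the assumed ranges the tabulated proportions are between unchanged and about 10% too low in relative terms, and 1% to about 14% of patients with an event go unseen. Rare serious reactions and deaths, where single cases count, are where this would matter most.

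A reader might multiply an assumed ineligible share by the planning bleeding rates and quote a number of missing reactions. The documents do not support this. Those rates belong to the primary bleeding outcome analysed under SAP 7.6, only bleeds judged drug-related enter the ADR tables, and the ineligible share is a guess. Nor do the documents show that the removed patients are at higher risk or that the profile is distorted in a known direction.

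**What to change.** In SAP 6.3 add a fourth set, TREATED: consented Objective 2 patients with at least one intake of DE or VKA, regardless of eligibility. Produce the 7.9.1 ADR and fatal event tables, with their person-years, on this set alongside the existing tables for eligible treated patients. By treatment group, report the number of treated patients judged ineligible, and list their ADRs and deaths. Leave the comparative outcome analyses on the eligible and restricted sets. Check the Protocol Deviation Specification for any handling rule and align it.

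The cost is SAP wording and a second run of the tables; no new data are needed. The downsides are a safety denominator slightly different from that of the outcome tables, and possibly truncated follow-up for patients withdrawn as erroneously included, which a footnote can state.
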